APPENDIX 2. PARTIAL DATE CONVENTIONS

Imputed dates will NOT be presented in the listings.

ALGORITHM FOR TREATMENT EMERGENCE OF ADVERSE EVENTS

START DATE	STOP DATE	ACTION
Known	Known	If start date < study med start date, then not TEAE If start date >= study med start date, then TEAE
	Partial	If start date < study med start date, then not TEAE If start date >= study med start date, then TEAE
	Missing	If start date < study med start date, then not TEAE If start date >= study med start date, then TEAE
Partial, but known components show that it cannot be on or after study med start date	Known	Not TEAE
	Partial	Not TEAE
	Missing	Not TEAE
Partial, could be on or after study med start date	Known	If stop date < study med start date, then not TEAE If stop date >= study med start date, then TEAE
	Partial	Impute stop date as latest possible date (i.e. last day of month if day unknown or 31st December if day and month are unknown), then: If stop date < study med start date, then not TEAE

Document: Z:\RPL554\AZA40375\Biostatistics\Documentation\SAP\Verona RPL554-DP-201 SAP v1.0 – Part A

Author: [name]

Version Number: 1.0

Version Date: [19DEC2018]

Template No.: CS_TP_BS016 Revision 5

Reference: CS_WI_BS005

Effective Date: 01Apr2018

Copyright © 2009, 2010, 2012, 2016, 2018 IQVIA. All rights reserved. The contents of this document are confidential and proprietary to IQVIA Holdings Inc. and its subsidiaries. Unauthorized use, disclosure or reproduction is strictly prohibited.

START DATE	STOP DATE	ACTION
		If stop date \geq study med start date, then TEAE
	Missing	Assumed TEAE
Missing	Known	If stop date $<$ study med start date, then not TEAE If stop date \geq study med start date, then TEAE
	Partial	Impute stop date as latest possible date (i.e. last day of month if day unknown or 31st December if day and month are unknown), then: If stop date $<$ study med start date, then not TEAE If stop date \geq study med start date, then TEAE
	Missing	Assumed TEAE

ALGORITHM FOR PRIOR / CONCOMITANT MEDICATIONS

START DATE	STOP DATE	ACTION
Known	Known	If stop date $<$ study med start date, assign as prior If stop date \geq study med start date and start date \leq end of treatment, assign as concomitant If stop date \geq study med start date and start date $>$ end of treatment, assign as post study

Document: Z:\RPL554\AZA40375\Biostatistics\Documentation\SAP\Verona RPL554-DP-201 SAP v1.0 – Part A

Author: [name]

Version Number: 1.0

Version Date: [19DEC2018]

Template No.: CS_TP_BS016 Revision 5

Reference: CS_WI_BS005

Effective Date: 01Apr2018

Copyright © 2009, 2010, 2012, 2016, 2018 IQVIA. All rights reserved. The contents of this document are confidential and proprietary to IQVIA Holdings Inc. and its subsidiaries. Unauthorized use, disclosure or reproduction is strictly prohibited.

START DATE	STOP DATE	ACTION
	Partial	
Impute stop date as latest possible date (i.e. last day of month if day unknown or 31st December if day and month are unknown), then:
 
If stop date < study med start date, assign as prior
 
If stop date >= study med start date and start date <= end of treatment, assign as concomitant
 
If stop date >= study med start date and start date > end of treatment, assign as post treatment

	Missing	
If stop date is missing could never be assumed a prior medication
 
If start date <= end of treatment, assign as concomitant
 
If start date > end of treatment, assign as post treatment

Partial	Known	
Impute start date as earliest possible date (i.e. first day of month if day unknown or 1st January if day and month are unknown), then:
 
If stop date < study med start date, assign as prior
 
If stop date >= study med start date and start date <= end of treatment, assign as concomitant
 
If stop date >= study med start date and start date > end of treatment, assign as post treatment

Document: Z:\RPL554\AZA40375\Biostatistics\Documentation\SAP\Verona RPL554-DP-201 SAP v1.0 – Part A

Author: [name]

Version Number: 1.0

Version Date: [19DEC2018]

Template No.: CS_TP_BS016 Revision 5

Reference: CS_WI_BS005

Effective Date: 01Apr2018

Copyright © 2009, 2010, 2012, 2016, 2018 IQVIA. All rights reserved. The contents of this document are confidential and proprietary to IQVIA Holdings Inc. and its subsidiaries. Unauthorized use, disclosure or reproduction is strictly prohibited.

START DATE	STOP DATE	ACTION
	Partial	Impute start date as earliest possible date (i.e. first day of month if day unknown or 1st January if day and month are unknown) and impute stop date as latest possible date (i.e. last day of month if day unknown or 31st December if day and month are unknown), then: If stop date < study med start date, assign as prior If stop date >= study med start date and start date <= end of treatment, assign as concomitant If stop date >= study med start date and start date > end of treatment, assign as post treatment
	Missing	Impute start date as earliest possible date (i.e. first day of month if day unknown or 1st January if day and month are unknown), then: If stop date is missing could never be assumed a prior medication If start date <= end of treatment, assign as concomitant If start date > end of treatment, assign as post treatment
Missing	Known	If stop date < study med start date, assign as prior If stop date >= study med start date, assign as concomitant Cannot be assigned as 'post treatment'
	Partial	Impute stop date as latest possible date (i.e. last day of month if day unknown or 31st December if day and month are unknown), then: If stop date < study med start date, assign as prior If stop date >= study med start date, assign as concomitant Cannot be assigned as 'post treatment'
	Missing	Assign as concomitant

 Document: Z:\RPL554\AZA40375\Biostatistics\Documentation\SAP\Verona RPL554-DP-201 SAP v1.0 – Part A

Author: [name]

Version Number: 1.0

Version Date: [19DEC2018]

Template No.: CS_TP_BS016 Revision 5

Reference: CS_WI_BS005

Effective Date: 01Apr2018

Copyright © 2009, 2010, 2012, 2016, 2018 IQVIA. All rights reserved. The contents of this document are confidential and proprietary to IQVIA Holdings Inc. and its subsidiaries. Unauthorized use, disclosure or reproduction is strictly prohibited.

STATISTICAL ANALYSIS PLAN – PART B

RPL554-DP-201

A Phase II, Randomized Study to Assess the Pharmacokinetics, Safety and Pharmacodynamics of Single and Repeat Doses of RPL554 Administered by Dry Powder Inhaler in Patients with COPD

AUTHOR: [name] / [name]

VERSION NUMBER AND DATE: V2.0, 08JUL2019

Document: Z:\RPL554\AZA40375\Biostatistics\Documentation\SAP\Verona RPL554-DP-201 SAP v2.0 – Part B

Author: [name] / [name] Version Number: 2.0
Version Date: [08JUL2019]

Template No.: CS_TP_BS016 Revision 5 Reference: CS_WI_BS005

Effective Date: 01Apr2018

1. INTRODUCTION

This document describes the rules and conventions to be used in the presentation and analysis of efficacy, safety and pharmacokinetic (PK)/pharmacodynamic (PD) data for Part B of protocol RPL554-DP-201. It describes the data to be summarized and analyzed, including specifics of the statistical analyses to be performed. This statistical analysis plan (SAP) is based on the protocol version 2.0, dated 12FEB2019. The study will consist of two parts (A and B) and Part B will be described in this SAP. Only the protocol sections applicable to Part B will be described in this SAP.

2. STUDY OBJECTIVES FOR PART B

2.1. PRIMARY OBJECTIVE

The primary objective of Part B is to investigate the bronchodilator effect of repeat doses of RPL554 administered by DPI (Dry powder inhaler), assessed in terms of peak FEV₁ (forced expiratory volume in one second).

2.2. SECONDARY OBJECTIVES

The secondary objectives of this part are as follows:

- To investigate the safety and tolerability of repeat doses of RPL554 administered by DPI.
- To investigate the bronchodilator effect of RPL554 administered by DPI, in terms of average FEV₁ area under the curve (AUC)_{0-4h}, average FEV₁ AUC_{0-12h} and trough FEV₁.
- To determine the onset of action of RPL554 administered by DPI.
- To evaluate the PK profile of RPL554 administered by DPI.
- To evaluate the amount of rescue medication use during treatment periods.

2.3. EXPLORATORY OBJECTIVES

The exploratory objectives of this part are as follows:

Document: Z:\RPL554\AZA40375\Biostatistics\Documentation\SAP\Verona RPL554-DP-201 SAP v2.0 – Part B

Author: [name] / [name]

Version Number: 2.0

Version Date: [08JUL2019]

Template No.: CS_TP_BS016 Revision 5

Reference: CS_WI_BS005

Effective Date: 01Apr2018

Copyright © 2009, 2010, 2012, 2016, 2018 IQVIA. All rights reserved. The contents of this document are confidential and proprietary to IQVIA Holdings Inc. and its subsidiaries. Unauthorized use, disclosure or reproduction is strictly prohibited.

- To assess the dose response of RPL554 on peak and FEV₁ AUC_{0-12h} after morning dose on Day 7, and morning trough FEV₁ prior to the last dose on Day 7.
- To examine the effect of RPL554 administered by DPI on a Likert dyspnea scale.

3. STUDY DESIGN

3.1. GENERAL DESCRIPTION

This is a Phase II, randomized, double-blind, placebo-controlled, two-part study. Part A was a parallel group, single dose assessment of RPL554 administered by DPI to evaluate the safety and terminal PK profile of a range of doses of RPL554. Five dose levels, 150 µg, 500 µg, 1500 µg, 3000 µg and 6000 µg were selected, covering a 40-fold increase in doses. A total of approximately 36 COPD patients (as defined by the American Thoracic Society [ATS]/European Respiratory Society [ERS] guidelines with symptoms compatible with COPD for at least 1 year prior to Screening) aged 40 to 80 years (inclusive) were randomized at one site in the United States (US). At the end of Part A, the database was locked and the data unblinded and analyzed prior to commencing Part B. Four dose levels, 150 µg, 500 µg, 1500 µg, 3000 µg were selected for Part B, using the same Part A patients. Part B is designed as a crossover, repeat dose assessment of RPL554 administered by DPI to evaluate the steady state efficacy/PD effect of the four RPL554 doses compared to the effect with placebo DPI. The patients in Part B will be expected to complete five treatment periods.

In Part B, the patients from Part A will be randomly assigned in crossover fashion to one of 10 treatment sequences (see [Appendix 1](#); Presentation of Treatment Sequences) each consisting of five 1-week treatment periods separated by a 7 to 10-day washout. Each treatment period consists of 6 days of twice daily doses of RPL554, and a single morning dose on Day 7. In each treatment period, patients will undergo assessments over 12 hours on Days 1 and 7. Figure 1 below summarizes these details.

Document: Z:\RPL554\AZA40375\Biostatistics\Documentation\SAP\Verona RPL554-DP-201 SAP v2.0 – Part B

Author: [name] / [name]

Version Number: 2.0

Version Date: [08JUL2019]

[figure not shown]
Template No.: CS_TP_BS016 Revision 5

Reference: CS_WI_BS005

Effective Date: 01Apr2018

Copyright © 2009, 2010, 2012, 2016, 2018 IQVIA. All rights reserved. The contents of this document are confidential and proprietary to IQVIA Holdings Inc. and its subsidiaries. Unauthorized use, disclosure or reproduction is strictly prohibited.

Figure 1 Study Flow Chart

3.2. SCHEDULE OF EVENTS

Schedule of events can be found in Section 6 of the protocol.

3.3. CHANGES TO ANALYSIS FROM PROTOCOL

None.

4. PLANNED ANALYSES

There are no data monitoring committee (DMC) or formal interim analyses to be performed for this study. The study will consist of two separate and independent analyses, Part A and Part B. At the end of each part, the database will be locked and unblinded, and the analyses for each part will be performed.

4.1. DATA MONITORING COMMITTEE (DMC)

There will be no DMC analyses for this study.

4.2. INTERIM ANALYSIS

No formal interim analysis is planned for the study.

Document: Z:\RPL554\AZA40375\Biostatistics\Documentation\SAP\Verona RPL554-DP-201 SAP v2.0 – Part B

Author: [name] / [name]

Version Number: 2.0

Version Date: [08JUL2019]

Template No.: CS_TP_BS016 Revision 5

Reference: CS_WI_BS005

Effective Date: 01Apr2018

Copyright © 2009, 2010, 2012, 2016, 2018 IQVIA. All rights reserved. The contents of this document are confidential and proprietary to IQVIA Holdings Inc. and its subsidiaries. Unauthorized use, disclosure or reproduction is strictly prohibited.

4.3. PART B ANALYSIS

All Part B analyses identified in this SAP will be performed by IQVIA Biostatistics following Database Lock on a clean database:

- All outstanding data issues and queries resolved.
- All irresolvable data issues documented in the Data Handling Report (DHR) from Data Management.
- All coding of medications, medical history and adverse events (AEs) completed.
- Serious AE (SAE) reconciliation completed.
- All reconciliation of vendor data with electronic case report form (eCRF) data completed successfully.
- Analysis sets authorized.

It should be noted that the main teams that performed the Part A analysis remained blinded at the time of the Part A database lock. This was to avoid any potential risk they could trace what study medication a patient might be receiving in Part B (e.g. if they know they experienced certain AEs while on one treatment in Part A and this was identifiable in Part B).

All verbatim text from the eCRF will be presented in outputs “as is” with no “manual hard coding” corrections for such data. Also, PK analysis will be performed by another party (third party vendor), and details of this analysis will not be specified in this SAP.

5. ANALYSIS SETS

Agreement and authorization of patients included/excluded from each analysis set will be conducted prior to the unblinding of the study for Part B.

In the case of dosing errors leading to duplication of treatment period or that treatment during period is undetermined, the period data for a patient could be excluded from the analysis. These will be agreed and documented prior to unblinding.

Document: Z:\RPL554\AZA40375\Biostatistics\Documentation\SAP\Verona RPL554-DP-201 SAP v2.0 – Part B

Author: [name] / [name]

Version Number: 2.0

Version Date: [08JUL2019]

Template No.: CS_TP_BS016 Revision 5

Reference: CS_WI_BS005

Effective Date: 01Apr2018

Copyright © 2009, 2010, 2012, 2016, 2018 IQVIA. All rights reserved. The contents of this document are confidential and proprietary to IQVIA Holdings Inc. and its subsidiaries. Unauthorized use, disclosure or reproduction is strictly prohibited.

5.1. PART A COMPLETERS SET

This set will contain all patients who completed Part A of the study.

5.2. ALL PATIENTS RANDOMIZED SET IN PART B [RND]

The all patients randomized (RND) set will contain all patients who completed Part A and who are randomized to study medication in Part B (two randomizations are expected for this study, one for each part). For analyses and displays based on RND, patients will be classified per randomized sequence/treatment.

5.3. SAFETY ANALYSIS SET [SAF]

The safety analysis set (SAF) will contain all patients in the RND set who received at least one dose of study medication during Part B. Patients will be classified per actual sequence/treatment received. If there is any doubt whether a patient was treated or not, they will be assumed treated for the purposes of analysis. If a patient is treated based on a non-pre-specified sequence, which is not one of the 10 listed treatment sequence, this will be reported as 'Undefined' for analysis by actual sequence/ treatment per [Appendix 1](#); Presentation of Treatment Sequences. For analysis by treatment group a patient should be counted once for each time a specific treatment was received.

5.4. FULL ANALYSIS SET [FAS]

The full analysis set (FAS) will contain all patients in the RND set with sufficient data (pre-dose and at least one post-dose assessment of spirometry) collected after intake of study medication to compute the pharmacodynamic parameters (FEV₁, FRC measurements) on at least 2 treatment periods in Part B. For analyses and displays based on FAS, patients will be classified per randomized sequence/treatment.

5.5. COMPLETERS ANALYSIS SET [CAS]

The completers analysis set (CAS) will contain all patients in the SAF analysis set who complete all treatment

Document: Z:\RPL554\AZA40375\Biostatistics\Documentation\SAP\Verona RPL554-DP-201 SAP v2.0 – Part B

Author: [name] / [name]

Version Number: 2.0

Version Date: [08JUL2019]

Template No.: CS_TP_BS016 Revision 5

Reference: CS_WI_BS005

Effective Date: 01Apr2018

Copyright © 2009, 2010, 2012, 2016, 2018 IQVIA. All rights reserved. The contents of this document are confidential and proprietary to IQVIA Holdings Inc. and its subsidiaries. Unauthorized use, disclosure or reproduction is strictly prohibited.

periods i.e., a patient who receives a first and last dose intake plus 1 day for all 5 treatment periods per schedule of events (see section 6 of the protocol for schedule details).

5.6. PHARMACOKINETICS [PK] ANALYSIS SET

The PK analysis set will contain all patients in the RND analysis set who have a blood sampling performed after at least one dose of RPL554 in Part B and with data sufficient to calculate PK parameter data.

6. GENERAL CONSIDERATIONS

6.1. REFERENCE START DATE AND STUDY DAY

Study day will be calculated from the reference start date (treatment period [TP] 1, day 1) and will be used to show start/stop day of assessments and events. Relative day will be calculated from the reference start date (each TP, day 1) and will be used to show start/stop day of assessments and events relative to each treatment period. Reference start date is defined as the day of the study medication and will appear in every listing where an assessment date or event date appears.

If the date of the event is on or after the reference date, then:

- Study day = (date of event – reference date) + 1.

If the date of the event is prior to the reference date, then:

- Study day = (date of event – reference date).

In the situation where the event date is partial or missing, the date will appear partial or missing in the listings, and study day, and any corresponding durations will be presented based on the imputations specified in [Appendix 2](#); Partial Date Conventions.

Document: Z:\RPL554\AZA40375\Biostatistics\Documentation\SAP\Verona RPL554-DP-201 SAP v2.0 – Part B

Author: [name] / [name]

Version Number: 2.0

Version Date: [08JUL2019]

Template No.: CS_TP_BS016 Revision 5

Reference: CS_WI_BS005

Effective Date: 01Apr2018

Copyright © 2009, 2010, 2012, 2016, 2018 IQVIA. All rights reserved. The contents of this document are confidential and proprietary to IQVIA Holdings Inc. and its subsidiaries. Unauthorized use, disclosure or reproduction is strictly prohibited.

6.2. BASELINE

Baseline definitions are related to the treatment period the patient enters. For majority of endpoints (primary endpoint, relevant secondary/exploratory endpoints and safety endpoints assessed post-dose in the treatment periods), this will be the pre-dose assessment on Day 1 of each treatment period (treatment period 1 to treatment period 5). Baseline pre-dose FEV₁/FVC will be derived from 3 acceptable readings (performed up to 8 times to obtain these), with the highest result from each assessment being used for analysis. For safety assessments with pre-dose assessments, baseline will be defined as the pre-dose assessment for each treatment period.

6.3. REPEAT/RESCHEDULE, UNSCHEDULED VISITS AND EARLY TERMINATION DATA

In general, for by-visit summaries, data recorded at the nominal visit will be presented. If a visit is repeated/rescheduled due to variability in FEV₁ or other reason, the repeated/rescheduled visit, will be listed and summarized as the valid visit (same visit number assigned). Unscheduled measurements will not be included in by-visit summaries, but will contribute to the endpoint value. For example, if an unscheduled visit occurred at 10 hours post-dose on Day 1, then this value will be considered in the calculation of the average FEV₁ over 12 hours (AUC_{0-12h} FEV₁). Any unscheduled or unplanned readings will be presented within the patient listings.

Early termination data will be mapped according to the visit number the termination occurred for by-visit summaries. If termination is between the end of Part A and the beginning of Part B, data are to be considered in the Part B SAP and patient is considered a Part A completer.

Listings will include scheduled, unscheduled, repeat/reschedule and early discontinuation data.

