9.4.5 Efficacy/Pharmacodynamics

FEV₁ and FVC will be summarized as actual value and change from baseline using descriptive statistics over time for all treatments and both study parts.

The peak effect on FEV₁ during these time intervals will be computed as the maximum value in the 4 hours after dosing. The average effect (average FEV₁ AUC_{0-t}) will be calculated as the AUC divided by the length of the time interval of interest. For analysis of the peak, average and trough FEV₁, the change from baseline will be expressed as the parameter divided by the pre-dose Day 1 baseline value.

In Part A, computed pharmacodynamic parameters for FEV₁ will be compared between the treatments using analysis of covariance models with fixed factor treatment, and using the pre-dose baseline value as a covariate. In Part B, computed pharmacodynamic parameters (peak, AUC₀₋₄, AUC₀₋₁₂ and trough) for FEV₁ will be compared between the treatments using analysis of covariance models adjusting for treatment period and patient, and using the pre-dose Day 1 baseline value as a covariate. FEV₁ will be analyzed using multiplicative models, which means that data (dependent and baseline) are logged prior to analysis and the result then transformed back to the linear scale giving treatment differences as ratios of geometric means.

Primarily, active treatments will be compared to placebo. For RPL554 DPI, the high dose will first be compared to placebo, and if found statistically significant then the next lower dose will be compared to placebo, and if found statistically significant then the subsequent lower dose will be compared to placebo, and this procedure repeated for all doses. Secondarily, the different doses of RPL554 DPI will be compared. Results of the comparisons will be expressed as the mean geometric ratio with 95% confidence intervals and associated, 2-sided, p-value.

Onset of action will be calculated and summarized by treatment. In Part B, a Kaplan-Meier plot illustrating time to onset will be constructed and from the survival curves the median time to onset will be estimated. Placebo will not be included in summaries of onset of action.

In Part B, the average use of rescue medication during the treatment periods will be summarized by treatment group. In addition, all rescue medication used during the treatment visits (Day 1 in Part A and Days 1 and 7 in Part B) will be listed to assess the accuracy of the FEV₁ recordings.

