9.4.8 Handling of Withdrawals or Missing Data

In Part B, patients withdrawn after only one treatment period will not be included in the efficacy/pharmacodynamic and PK analyses of parameters that can be computed in all planned treatment periods. Imputation of data for calculation of average (AUC) effects for FEV₁ will be described in the statistical analysis plan. No other imputation of missing data will be performed.

All available data from all dosed patients who have received study treatment will be listed and summarized. Any unscheduled or unplanned readings will be presented within the patient listings, but only the scheduled readings will be used in any summaries. If a visit is rescheduled

due to variability in FEV₁ or other reason, the rescheduled visit will be listed and summarized as the valid visit.

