Copyright © 2009, 2010, 2012, 2016, 2018 IQVIA. All rights reserved. The contents of this document are confidential and proprietary to IQVIA Holdings Inc. and its subsidiaries. Unauthorized use, disclosure or reproduction is strictly prohibited.

15.2.1.3. Change from baseline in peak FEV₁ (measured in first 4 hours) after single dose (Secondary variable 3)

Peak FEV₁ is measured in the first 4 hours after single dose. It is collected on the Spirometry Study measurements eCRF page.

Three acceptable readings are performed at each of the timepoints in first 4 hours after the single dose (5, 15 and 30 minutes and 1, 1.5, 2 and 4 hours) and the highest of the 3 is used for analysis purposes. Hence peak FEV₁ is derived as the highest of all these readings.

Descriptive statistics (see [Appendix 1](#) [Programming conventions for outputs]) for peak FEV₁ will be presented for all patients assigned to FAS, at each assessment and change from baseline as relevant. All summaries will be presented for each treatment group. In addition, a figure (bar graph) representing mean change from baseline FEV₁ to peak FEV₁ by treatment will be presented, including the standard error of the mean. A figure also displaying the mean change over time on Day 1 will be presented.

Change from baseline FEV₁ to peak FEV₁ (over 4 hours) will be derived to test the hypothesis described in [Section 15.2.3](#) with baseline defined as the average of the FEV₁ pre-dose assessments (-60 minutes and -5 minutes) collected.

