6.6. COMMON CALCULATIONS

Assessments assigned to treatment periods:

- Based on the day of assessment relative to the start date of each treatment period as defined by the first treatment administration for that specific treatment period:
 - Treatment period 1
 - Treatment period 2
 - Treatment period 3
 - Treatment period 4
 - Treatment period 5

For quantitative measurements, change from baseline will be calculated as:

- Test value at post-dose timepoint – baseline value.

For quantitative measurement values of FEV₁ and FEV₁ AUCs will be calculated based on:

- The highest FEV₁ reading from each assessment.
- The baseline value (average of the two pre-dose values [at 1-hour {±5 minutes} and immediately {within 5 minutes} } pre-dose) must be within ± 20% of the pre-albuterol value at Screening; otherwise, the patient will be a screen failure.

Peak effect will be calculated as:

- Maximum value in the first 4 hours after dosing.

Average effect will be calculated as:

- FEV₁ AUC divided by the length of the time interval of interest.

Document: Z:\RPL554\AZA40375\Biostatistics\Documentation\SAP\Verona RPL554-DP-201 SAP v2.0 – Part B

Author: [name] / [name]

Version Number: 2.0

Version Date: [08JUL2019]

Template No.: CS_TP_BS016 Revision 5

Reference: CS_WI_BS005

Effective Date: 01Apr2018

Copyright © 2009, 2010, 2012, 2016, 2018 IQVIA. All rights reserved. The contents of this document are confidential and proprietary to IQVIA Holdings Inc. and its subsidiaries. Unauthorized use, disclosure or reproduction is strictly prohibited.

Log-transformations will be performed on FEV₁ data:

- FEV₁ will be analyzed using multiplicative models, which means that data will be logged prior to analysis. The results will then be back-transformed to linear scale (treatment differences will thus be ratios of geometric means).

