15. EFFICACY OUTCOMES

15.1. PRIMARY EFFICACY

15.1.1. PRIMARY EFFICACY VARIABLE(S) & DERIVATION(S)

The primary efficacy variable is peak FEV₁ (measured in first 4 hours after morning dosing). This will be measured after dosing on Day 7 and is collected on the Spirometry Study measurements eCRF page. The primary efficacy endpoint is change from baseline in peak FEV₁.

Three acceptable readings are performed at each of the timepoints in first 4 hours after morning dosing on Day 7 (5, 15 and 30 minutes and 1, 1.5, 2 and 4 hours) and the highest of the 3 is used for analysis purposes. Hence, peak

Document: Z:\RPL554\AZA40375\Biostatistics\Documentation\SAP\Verona RPL554-DP-201 SAP v2.0 – Part B

Author: [name] / [name]

Version Number: 2.0

Version Date: [08JUL2019]

Template No.: CS_TP_BS016 Revision 5

Reference: CS_WI_BS005

Effective Date: 01Apr2018

Copyright © 2009, 2010, 2012, 2016, 2018 IQVIA. All rights reserved. The contents of this document are confidential and proprietary to IQVIA Holdings Inc. and its subsidiaries. Unauthorized use, disclosure or reproduction is strictly prohibited.

FEV₁ is derived as the highest of all these readings. Patients withdrawn after only one treatment period will not be included in the analysis.

Descriptive statistics (see [Appendix 1](#) [Programming conventions for outputs]) for FEV₁ will be presented for all patients assigned to FAS, at each assessment and change from baseline at each assessment. All summaries will be presented for each treatment group by day and timepoint. In addition, a figure (bar graph) representing mean change from baseline FEV₁ to peak FEV₁ by treatment will be presented, including the standard error of the mean.

Change from baseline FEV₁ to peak FEV₁ (over 4 hours) at Day 7 will be derived to test the hypothesis described in [section 15.1.3](#) with baseline defined as the average of the FEV₁ pre-dose assessment (-60 minutes and -5 minutes) collected on Day 1 of each treatment period. Peak FEV₁ at Day 7 is defined as the maximum post-dose value among the 5, 15, 30 minutes, 1, 1.5, 2 and 4-hour assessments collected at after morning dose on Day 7 of each treatment period.

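### SAP 6.3 lets unscheduled FEV₁ readings into endpoint values, an undeclared conflict with protocol 9.4.8 that is explicit for AUC0-12h and leaves the peak FEV₁ derivation internally inconsistent

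*SAP*

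**What the plan says.** Protocol 9.4.8 sets the rule: "Any unscheduled or unplanned readings will be presented within the patient listings, but only the scheduled readings will be used in any summaries". Protocol 6 leaves unscheduled procedures to the investigator's discretion.

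Section 6.3 of the Part A and Part B SAPs restricts the exclusion to by-visit summaries and then goes the other way for endpoints: "Unscheduled measurements will not be included in by-visit summaries, but will contribute to the endpoint value". The Part B example is explicit for the 12-hour AUC: "if an unscheduled visit occurred at 10 hours post-dose on Day 1, then this value will be considered in the calculation of the average". Part A gives the same example for the single-dose day.

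For peak FEV₁ there are two kinds of definition:
- **General.** Protocol 9.4.5 has it "computed as the maximum value in the 4 hours after dosing". SAP 6.6 has "Maximum value in the first 4 hours after dosing". Neither names timepoints.
- **Endpoint-specific.** Part B 15.1.1 defines the Day 7 peak as the "maximum post-dose value among the 5, 15, 30 minutes, 1, 1.5, 2 and 4-hour assessments". Part A 15.2.1.3 lists the same seven times and concludes: "Hence peak FEV₁ is derived as the highest of all these readings".

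On changes to the analysis from the protocol, section 3.3 reads as not applicable in Part A and as none in Part B.

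**The concern.** Two separate faults follow.

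First, the SAPs depart from the protocol without saying so. Derived peak and AUC values are themselves summarised by treatment (Part A 15.2.3; Part B 15.1.3 and 15.2.3.1). An unscheduled reading inside a derived value therefore reaches a summary that the protocol restricts to scheduled readings.

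Second, two programmers could derive different values of the Part B primary endpoint from the same data. One would follow 6.3 and 6.6, the other 15.1.1.

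At stake is an endpoint that depends partly on how often, and when, an investigator chose to measure a patient. A maximum responds to this in one direction only. A trapezoid average can respond in either.

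**Working it through.** **Plan's own figure.** Protocol 9.5 gives 30 patients, residual CV 6%, 80% power, a 4.6% difference and a 1.5 L baseline; tests are two-sided at 5% (9.4).
- Log-scale SD = √ln(1 + 0.06²) = 0.0599; SE = 0.0599 × √(2/30) = 0.0155; δ = ln(1.046) = 0.0450.
- Noncentral t with 29 df gives 80.2% power, so the stated figure reproduces.
- 4.6% × 1.5 L = 69 mL, the yardstick below.

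**AUC0-12h.** Part B Day 1 spirometry is scheduled at 8 and 12 hours with nothing between (protocol 6.4.1.3).
- Without a 10-hour reading the last trapezoid is 2y₈ + 2y₁₂. With one it is y₈ + 2y₁₀ + y₁₂.
- The difference is 2[y₁₀ − (y₈ + y₁₂)/2]. Divided by 12 hours, the extra reading's distance from the 8-12 hour line has weight 2/12.
- A reading 150 mL off that line (an illustrative size) moves the average by 150 × 2/12 = 25 mL, up or down.
- On Day 7, with readings at 8 and 11 hours, the weight is 1.5/12, so the same reading moves the average by 18.75 mL.
- In simulation with an assumed bronchodilator profile and reading SD of 3% or 6%, adding a 10-hour reading on Day 1 changed the mean by −0.3 mL (per-patient SD 9 and 18 mL). There is no inherent upward bias.

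**Peak, if 6.3 and 6.6 govern.** Five readings are scheduled within 4 hours on Day 7 (0.5, 1, 1.5, 2 and 4 hours; protocol 6.4.2.3).
- For independent normal readings on a flat profile, the expected maximum in SD units is 1.163 for five readings, 1.267 for six and 1.352 for seven.
- One extra reading adds 1.267 − 1.163 = 0.104 SD.
- The documents give no within-visit SD for a single reading. I assume 2% to 6%, the upper end being the residual CV.

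| Assumed reading SD | One extra reading | Two extra readings |
|---|---|---|
| 2% | 0.21% (3.1 mL) | 0.38% (5.7 mL) |
| 3% | 0.31% (4.7 mL) | 0.57% (8.5 mL) |
| 6% | 0.63% (9.4 mL) | 1.14% (17.0 mL) |

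These are shifts per affected patient-visit at 1.5 L. Timing matters: with an assumed profile highest at 1 to 1.5 hours and a 3% SD, one extra reading at 1.25 hours adds 0.53% (8.0 mL), and one at 3 hours adds 0.10% (1.5 mL). With seven scheduled readings, as on Day 1 and in Part A, the flat-profile gain at 3% is 3.2 mL.

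**Contrast.** Only the difference between treatments in the share of patients with an extra reading matters. One extra reading, flat profile, 3% SD:
- 10% imbalance: 0.1 × 4.7 = 0.5 mL; two-sided type I error 5.0%.
- 50% imbalance: 2.3 mL; 5.1%.
- 100% imbalance: 4.7 mL; 5.5%.
- At 6% SD, with every patient affected on one treatment only: 9.4 mL; 6.9%.

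**The case against.** Four arguments have weight.

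- **A specific definition normally overrides a general one.** The endpoint sections name the times, and the only example in 6.3 is AUC0-12h. This stands to the extent that peak cannot be said to include unscheduled readings. But 6.3 speaks of the endpoint value without exempting peak, and 6.6 states no timepoints, so the inconsistency remains.
- **Protocol 9.4.8 speaks of summaries, not derivations.** Reading it as a scheduled-only rule for endpoints is an interpretation. It is a reasonable one because the derived values are summarised. The section also leaves imputation for FEV₁ AUC to the SAP, but it does not delegate the use of unscheduled readings.
- **A genuine 10-hour value is defensible in a time-weighted average** when the neighbouring readings are four hours apart. That is true, but it is then a departure to be declared.
- **The effect is small.** The arithmetic agrees.

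A reader might go further and infer that peak is certainly biased upward, that extra readings would cluster on placebo, or that post-rescue readings would lift the placebo mean by a predictable amount. The documents do not support any of these. They give no frequency of unscheduled readings and no split by treatment. A reading taken because of symptoms would tend to be low, could not raise a maximum and would lower an AUC. The 150 mL reversibility criterion is a minimum rise from pre-bronchodilator FEV₁, not an increment over the best of several post-dose readings. Protocol 5.8.1 also withholds short-acting bronchodilators until after the 12-hour spirometry. If rescue is taken anyway, later scheduled readings can carry its effect too, so a scheduled-only rule would not remove it.

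**Conclusion.** The concern holds as a conflict between documents and within the SAPs. SAP 6.3 contradicts protocol 9.4.8 explicitly for AUC0-12h, and neither SAP declares it. For peak FEV₁, 6.3 and 6.6 point one way and the endpoint sections the other. If extra readings are admitted, peak can only stay or rise, while AUC can move either way.

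The likely effect on treatment contrasts is small: about 0.5 to 4.7 mL against 69 mL, on the assumptions of a 3% reading SD, a flat profile, one extra reading and a 10% to 100% imbalance. Because neither the imbalance nor the reading SD is known, this is a range of scenarios and not an estimate. The reason to act is that the primary endpoint should have one derivation, fixed before unblinding and independent of discretionary measurement.

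**What to change.** **Part B SAP.** In 6.3, state that unscheduled measurements are listed only and enter neither by-visit summaries nor derived endpoints (peak, AUC, trough, onset). Delete the 10-hour example. Leave the rule on repeated or rescheduled visits as it is. Align 6.6 with the scheduled timepoints in 15.1.1. While doing so, reconcile the 15.1.1 list with protocol 6.4.2.3 and Table 6, because it includes 5 and 15 minutes, which the protocol does not schedule on Day 7.

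**Alternative.** If the sponsor prefers to use unscheduled readings, declare it in 3.3, say which endpoints it covers, and add a scheduled-only sensitivity analysis.

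**Part A.** This part is already analysed. Report the departure and any affected peak or AUC values in the clinical study report, where protocol 9.1 requires deviations from the specified analysis to be detailed and justified.

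**Cost.** A few sentences in the Part B SAP, to be settled before Part B is unblinded. The readings stay in the listings, and the sample size and power are unchanged.
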